8.1 Sample Size Determination

Currently, there is only little reliable data describing the percentage of patients with melanoma progressing after prior therapy containing treatment with an anti-CTLA-4 monoclonal antibody, presenting with Performance Status 2, and eligible for nivolumab treatment. It is estimated that a minimum of 20% of the potential study population will initially present with PS2. Given that 20% of the 920 patients screened is 185 patients, it is expected that the full complement of 160 patients will be enrolled into the PS2 cohorts and treated.

With an approximate 15% screening failure rate, a cohort of 735 enrolled PS1 patients is projected to a yield 640 treated patients. With $n = 640$ patients, about 3 will experience a rare adverse event with 0.5% true cumulative event rate with a rate estimated within 95% confidence interval (CI) (0.1%-1.4%). Approximately 2 patients with events and a 95% CI of (0%-1.1%) for assumed true event rate of 0.3% are projected.

8.2 Populations for Analyses

- The safety analysis set comprises patients who received at least 1 dose of nivolumab. The analysis of safety, OS, and QoL data will be based on the safety analysis set.
- The response evaluable analysis set comprises patients who received at least 1 dose of nivolumab and have both baseline and at least 1 post-baseline tumor scan.

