xv) Patients must have evaluable disease by CT or MRI per RECIST 1.1 criteria (radiographic tumor assessment performed within 6 weeks of first dose of study drug) or clinically apparent disease that the investigator can follow for response.

xvi) Patient Re-enrollment: This study permits the re-enrollment of a subject that has discontinued the study as a pre-treatment failure (ie, subject has not been treated). If re-enrolled, the subject must be re-consented.

b) As of Amendment 03, this criterion is not applicable.

- i) As of Amendment 03, this criterion is not applicable.
- ii) As of Amendment 03, this criterion is not applicable.
 - (1) As of Amendment 03, this criterion is not applicable.
 - (2) As of Amendment 03, this criterion is not applicable.
- iii) As of Amendment 03, this criterion is not applicable.
 - (1) As of Amendment 03, this criterion is not applicable.
 - (2) As of Amendment 03, this criterion is not applicable.
 - (3) As of Amendment 03, this criterion is not applicable.
- iv) As of Amendment 03, this criterion is not applicable.
- v) As of Amendment 03, this criterion is not applicable.
- vi) As of Amendment 03, this criterion is not applicable.
- vii) As of Amendment 03, this criterion is not applicable.
- viii) As of Amendment 03, this criterion is not applicable.
 - (1) As of Amendment 03, this criterion is not applicable.
 - (2) As of Amendment 03, this criterion is not applicable.
 - (3) As of Amendment 03, this criterion is not applicable.
 - (4) As of Amendment 03, this criterion is not applicable.
 - (5) As of Amendment 03, this criterion is not applicable.
 - (a) As of Amendment 03, this criterion is not applicable.
 - (b) As of Amendment 03, this criterion is not applicable.
 - (6) As of Amendment 03, this criterion is not applicable.
 - (7) As of Amendment 03, this criterion is not applicable.
 - (8) As of Amendment 03, this criterion is not applicable.
- ix) As of Amendment 03, this criterion is not applicable.
- x) As of Amendment 03, this criterion is not applicable.
- xi) As of Amendment 03, this criterion is not applicable.

3. Age and Reproductive Status

- a) Men and women, aged ≥ 18 years

- b) Women of childbearing potential (WOCBP) must have a negative serum or urine pregnancy test (minimum sensitivity 25 IU/L or equivalent units of HCG) within 24 hours prior to the start of study drug.
- c) Women must not be breastfeeding

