4.6.5 Treatment Beyond Disease Progression

As described in [Section 1.1.2](#), accumulating evidence indicated a minority of patients treated with immunotherapy may derive clinical benefit despite initial evidence of progressive disease.³⁷

Patients treated with nivolumab will be permitted to continue treatment beyond initial Investigator-assessed progressive disease as long as they meet the following criteria:

- Investigator-assessed clinical benefit and do not have rapid disease progression
- Tolerance of study drug
- Stable performance status
- Treatment beyond progression will not delay an imminent intervention to prevent serious complications of disease progression (eg, CNS metastases)
- Patient provides written informed consent prior to receiving additional nivolumab treatment using an ICF describing any reasonably foreseeable risk or discomforts or other alternative treatment options
- The assessment of clinical benefit should be balanced by clinical judgment as to whether the patient is clinically deteriorating and unlikely to receive any benefit from continued treatment with nivolumab

If the investigator feels that the nivolumab patient continues to achieve clinical benefit by continued treatment, the patient should remain on the trial and continue to receive monitoring according to the Time and Events Schedule in [Table 5.1-2](#).

Global deterioration of health status requiring discontinuation of treatment without objective evidence of disease progression at the time should be reported as symptomatic deterioration. Every effort should be made to document objective progression (ie, radiographic confirmation) even after discontinuation of treatment.

The assessment of clinical benefit should take into account whether the patient is clinically deteriorating and unlikely to receive further benefit from continued treatment. All decisions to continue treatment beyond initial progression must be discussed in the study records.

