5.4 Efficacy Assessments

Efficacy assessments include initial mandatory tumor assessment at Week 12 (\pm 5 days). Further tumor assessments to be completed as required by local standards of care or at the investigator's discretion and are recommended every 8 weeks, as discussed in [Table 5.1-2](#).

Study evaluations will take place in accordance with [Table 5.1-2](#) and should be performed according to RECIST 1.1 criteria.

High resolution CT with oral or IV contrast or contrast-enhanced MRI are the preferred imaging modalities for assessing radiographic tumor response. If a patient has a known allergy to contrast material, please use local prophylaxis standards to obtain the assessment with contrast if at all possible or use an alternate modality. In cases where contrast is strictly contraindicated, a non-contrast scan will suffice. Screening assessments should be performed within 6 weeks prior to first dose of study drug. Brain MRI is the preferred imaging method for evaluating CNS metastasis, and an assessment is required during screening. If known or new CNS metastases are detected during screening, a brain scan is required at the mandatory tumor assessment at Week 12 (\pm 5 days). Furthermore, all known or suspected sites of disease should be assessed at screening and at subsequent assessments using the same imaging method and technique. If more than one method is used at screening, then the most accurate method according to RECIST 1.1 should be used when recording data and should again be used for all subsequent assessments. Bone scan, PET scan, or

ultrasound is not adequate for assessment of RECIST response. In selected circumstances where such modalities are the sole modality used to assess certain non-target organs, those non-target organs may be evaluated less frequently. For example, bone scans may need to be repeated only when complete response is identified in the target disease or when progression in bone is suspected. Previously treated CNS metastases are not considered measurable lesions for purposes of RECIST determined response.

Tumor measurements should be made by the same investigator or radiologist for each assessment whenever possible. Changes in tumor measurements and tumor responses to guide ongoing study treatment decisions should be assessed by the investigator using RECIST 1.1 at Week 12 and using investigator-assessed response thereafter.

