8.3.2 Secondary Endpoint(s)

The secondary endpoints include:

- Incidence of all high-grade (Grades 3 and higher), select adverse events
- Median time to onset and median time to resolution (Grades 3-4) of select adverse events
- OS is defined as the time from first dosing date to the date of death. A patient who has not died will be censored at last known date alive. OS will be followed continuously while patients are on treatment and every 3 months via in-person or phone contact after patients discontinue the study drug.

- Investigator-assessed ORR. ORR is defined as the number and percentage of patients with a best overall response (BOR) of confirmed CR or PR. ORR as assessed by the investigator will be reported.

[REDACTED]

[REDACTED]

[REDACTED]

[REDACTED]

[REDACTED]

[REDACTED]

[REDACTED]

[REDACTED]

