8.4 Analyses

The analysis of primary, secondary (excluding ORR), [REDACTED] will be reported for the full safety analysis set and by cohorts based on ECOG PS. ORR will be reported for the response evaluable analysis set and by PS. OS and ORR will be further presented by initial investigator-assessed objective response under treatment with an anti-CTLA-4 monoclonal antibody.

Additional details regarding statistical analyses performed in the study are provided in the Statistical Analysis Plan (SAP), which will be finalized before data base lock.

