7.5 Efficacy

7.5.1 Overall Survival and Overall Response Rate at Week 12

Overall survival is defined as the time between the start of treatment and the date of death due to any cause. A subject who has not died will be censored at last known date alive.

Overall survival will be summarized using Kaplan-Meier (KM) product-limit method and associated statistics in the all treated analysis set by subpopulations. Median values of OS, if estimable, along with 2-sided 95% CI using the Brookmeyer and Crowley method will be calculated. If medians are not estimable, other percentiles (e.g., 10th and 25th) may be reported. OS

rates at selected time points, including survival rates at 6 months, 12 months, 18 months, and 24 months, together with their 95% CIs will also be estimated using KM estimates on the OS curves. Minimum follow-up must be longer than the timepoint of interest to generate the OS rate for that particular timepoint. For example, if the timepoint of interest is 6 months and the interval of enrollment date and last patient last visit is less than 6 months, then, the minimum follow-up is not reached and OS rate is not generated. Associated 2-sided 95% CIs will be calculated using the Greenwood formula.

A swimming plot showing the response, progression, duration of therapy and death will be presented using the all treated analysis set, overall and by ECOG PS 2, Ocular/Uveal, and Mucosal subpopulations only.

The overall response rate is defined as the number of subjects with a complete response (CR) or partial response (PR) at week 12 divided by the number of subjects treated. The overall response will be summarized by binomial response rates and their corresponding two-sided 95% exact CIs using the Clopper-Pearson method. A by subject listing will be provided.

A summary of overall response will also be presented by baseline LDH, BRAF status, and type of autoimmune disorder.

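### The protocol's ORR omits treated patients never scanned after baseline, which biases it upward; the SAP's all-treated denominator belongs to a different response measure

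*Protocol*

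**What the plan says.** **Numerator.** Protocol 8.3.2: "ORR is defined as the number and percentage of patients with a best overall response (BOR) of confirmed CR or PR", as assessed by the investigator.

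**Denominator.** Protocol 8.4: "ORR will be reported for the response evaluable analysis set and by PS". Protocol 8.2 defines that set as "patients who received at least 1 dose of nivolumab and have both baseline and at least 1 post-baseline tumor scan".

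**Scan schedule.** Protocol 5.4: "Efficacy assessments include initial mandatory tumor assessment at Week 12", with a window of ± 5 days. Later on-treatment scans follow local practice and are recommended every 8 weeks. Table 5.1-3 recommends off-treatment scans according to local standards or the investigator's discretion. For patients who stop because of symptomatic deterioration, Protocol 4.6.5 adds: "Every effort should be made to document objective progression (ie, radiographic confirmation) even after discontinuation of treatment".

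**SAP.** Section 7.5.1 counts complete response or "partial response (PR) at week 12 divided by the number of subjects treated", with Clopper-Pearson intervals. Section 6.4 makes all treated subjects the default set. Section 6.3 still defines the response evaluable set, but 7.5.1 does not use it for response.

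**The concern.** Whether a patient enters the protocol's ORR denominator depends on something that happens after treatment starts. No scan is mandatory before Week 12, and none is mandatory after early stopping. A treated patient who dies or declines early can therefore have no post-baseline scan at all. Such a patient is most naturally a treatment failure, yet the protocol removes the patient from the denominator. The result is an ORR among those who lasted long enough to be scanned, presented as the trial's secondary ORR.

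The trial admits PS 2 patients, and the protocol sets a minimum life expectancy only for those with leptomeningeal disease, so early losses are foreseeable. Because ORR is also reported by PS, each cohort's figure carries its own unknown degree of selection.

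**Working it through.** **1. The documents' own figures.** Neither document states a target, expected value or precision for ORR. The nearest usable figure is in Protocol 1.4.1.1, for the sequenced regimen of the Phase 1b study: 6 of 30, 20%, 95% CI 8 to 39. Clopper-Pearson gives 7.7% to 38.6%, so it reproduces. The same section says 33 patients received that regimen: 6/33 = 18.2% (7.0% to 35.5%), and the ratio is 33/30 = 1.10. The text does not say why three patients are not counted. The example shows only that the denominator matters.

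**2. Formula.** Let N be treated patients, R responders and q the share with no post-baseline scan. Assume no unscanned patient is a responder.

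- All-treated ORR = R/N
- Response evaluable ORR = R/[N(1−q)] = (R/N) × 1/(1−q)
- Excess in percentage points = (R/N) × q/(1−q)

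**3. Inflation factor.** The documents give no q, so it is varied as an assumption.

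| q | 1/(1−q) |
|---|---|
| 5% | 1.05 |
| 10% | 1.11 |
| 20% | 1.25 |
| 30% | 1.43 |

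**4. A rough anchor for q.** Protocol 1.4.1 cites a 1-year survival of 62% in an earlier melanoma study. Under a constant hazard, deaths by Week 12 are 1 − 0.62^(84/365.25) = 10.4%. If none of these patients had been scanned, the factor would be 1/(1 − 0.104) = 1.12. At that death rate this is the most that deaths alone could add, because some of those who died may have been scanned. The earlier study pooled several doses and is specific neither to this trial's patients nor to PS 2.

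**5. In the planned cohort sizes.** Protocol Section 8 plans 640 treated PS 0-1 patients and 160 PS 2 patients. The all-treated ORRs below are assumptions, borrowed from the 32% (Phase 3) and 20% (Phase 1b) cited in Protocol 1.4.1.1. Intervals are Clopper-Pearson.

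| Cohort | q | All treated | Response evaluable |
|---|---|---|---|
| PS 0-1 | 10% | 205/640 = 32.0% (28.4–35.8) | 205/576 = 35.6% (31.7–39.7) |
| PS 2 | 20% | 32/160 = 20.0% (14.1–27.0) | 32/128 = 25.0% (17.8–33.4) |
| PS 2 | 30% | 32/160 = 20.0% (14.1–27.0) | 32/112 = 28.6% (20.4–37.9) |

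**6. Effect on the difference between cohorts.** The direction is not fixed.

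- PS 0-1 at 32% with q = 10%, PS 2 at 20% with q = 30%: the gap shrinks from 12.0 points to 35.6 − 28.6 = 7.0.
- PS 0-1 at 32% with q = 10%, PS 2 at 10% with q = 20%: the gap widens from 22.0 points to 35.6 − 12.5 = 23.1, although PS 2 loses twice the share.

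**7. Protocol against SAP.** The protocol pairs confirmed best overall response with the response evaluable set. The SAP pairs response at Week 12 with all treated subjects. Neither document, as readable, pairs confirmed best response with all treated patients. With the all-treated denominator the inflation is zero for any q.

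**The case against.** The strongest reply is that the SAP already uses the right denominator: 7.5.1 divides by all treated, 6.4 makes that the default, and Protocol 8.4 leaves further analysis detail to the SAP. This stands for the SAP's own response rate, which is not inflated by missing scans. It does not settle the protocol's endpoint. Response at Week 12 is a different quantity from confirmed best response, and the only denominator the protocol gives for the latter is the response evaluable set. Parts of the SAP's endpoint section are blacked out, so this statement covers the readable text only.

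A second reply is that any post-baseline scan keeps a patient in the set, including an unscheduled one or one after stopping. Protocol 4.6.5 urges such scans, and Sections 4.6.1.1 and 4.6.4 continue tumor assessments while dosing is interrupted. This also stands. Early progression or toxicity does not by itself exclude anyone; only patients never scanned are lost, so q may be well below the early failure rate.

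Three stronger readings are tempting but not supported:

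- **That patients followed clinically have no scans.** Entry is allowed with RECIST-evaluable disease on CT or MRI "or clinically apparent disease that the investigator can follow for response". That concerns which disease qualifies. Table 5.1-1 schedules baseline imaging, and Table 5.1-2 the Week 12 assessment, with no exemption for these patients.
- **That the comparison of PS cohorts is a main question of the trial.** The readable objectives contain no such comparison, and no between-cohort response test is described.
- **That the PS difference is necessarily pulled toward zero.** Step 6 of the working shows that it can move either way.

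**Conclusion.** The point holds for the protocol's secondary ORR. Followed as written, Protocol 8.2 and 8.4 give a rate biased upward by 1/(1−q), provided some treated patients are never scanned and none of them is a responder. The size is unknown because the documents give no q. Over an assumed 5% to 30% the factor runs from 1.05 to 1.43; the 62% one-year survival supports at most about 1.12 from deaths alone, under the assumptions in step 4.

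A reader might infer that PS 2 is inflated most. In relative terms that is true only if q is larger there. This is plausible, but neither document gives early death or missing-scan rates by PS.

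Separately, the two documents conflict on both the denominator and the numerator of the response rate, and this needs to be reconciled whatever q turns out to be. The primary safety endpoint and the sample size are unaffected. ORR is a descriptive secondary endpoint, so this is a correction worth making rather than a threat to the trial's main result.

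**What to change.** In Protocol 8.2 and 8.4 and in SAP 7.5.1:

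- Report confirmed ORR (best overall response of CR or PR), overall and by PS, on all treated patients. Count a patient with no post-baseline assessment as a non-responder.
- Show both PS cohorts. SAP 7.1 lists an ECOG PS 2 column but none for PS 0-1.
- Keep the response evaluable result as a labelled supportive analysis. For each cohort, give the number of treated patients excluded and the reason (death, deterioration, toxicity, withdrawal, other).
- If the SAP's Week 12 response rate is retained, label it as a separate measure.

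The cost is wording in the two documents and one disposition table; no new data are needed. The downside is a somewhat lower headline ORR. SAP 7.5.1 already divides by all treated subjects, so the denominator should be acceptable to the sponsor.

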8.3 Endpoints

8.3.1 Primary Endpoint(s)

The primary endpoint is the incidence for high-grade (CTCAE v4.0 Grade 3 or higher), treatment-related, select adverse events.

Select adverse events are defined in [Section 4.6.1.1](#).

8.3.2 Secondary Endpoint(s)

The secondary endpoints include:

- Incidence of all high-grade (Grades 3 and higher), select adverse events
- Median time to onset and median time to resolution (Grades 3-4) of select adverse events
- OS is defined as the time from first dosing date to the date of death. A patient who has not died will be censored at last known date alive. OS will be followed continuously while patients are on treatment and every 3 months via in-person or phone contact after patients discontinue the study drug.

- Investigator-assessed ORR. ORR is defined as the number and percentage of patients with a best overall response (BOR) of confirmed CR or PR. ORR as assessed by the investigator will be reported.

[REDACTED]

[REDACTED]

[REDACTED]

[REDACTED]

[REDACTED]

[REDACTED]

[REDACTED]

[REDACTED]

8.4 Analyses

The analysis of primary, secondary (excluding ORR), [REDACTED] will be reported for the full safety analysis set and by cohorts based on ECOG PS. ORR will be reported for the response evaluable analysis set and by PS. OS and ORR will be further presented by initial investigator-assessed objective response under treatment with an anti-CTLA-4 monoclonal antibody.

Additional details regarding statistical analyses performed in the study are provided in the Statistical Analysis Plan (SAP), which will be finalized before data base lock.

8.4.1 Demographics and Baseline Characteristics

The demographic characteristics, medical history, and baseline assessments of patients will be reported as counts and percentages. The number and percentage of patients by cohorts and subgroups based on types of melanoma (with BRAF-mutated melanoma, uveal melanoma, mucosal melanoma), patients with CNS metastases, patients with known autoimmune disease, and patients who experienced immune-related adverse events during treatment with an anti-CTLA-4 antibody will be presented.

Study participation status including completion and discontinuation of treatment will be reported. Reasons for discontinuation will be summarized.

8.4.2 Safety Analyses

8.4.2.1 Primary Analyses

The evidence for the research hypothesis of this clinical trial that high-grade (CTCAE v4.0 Grade 3 or higher), treatment-related select adverse events occur with a low frequency in patients with advanced (unresectable or metastatic) melanoma will be presented in terms of the number, percentage of patients, and 95% confidence intervals for the percentage with these select adverse events during and off-treatment overall and by cohort.

8.4.2.2 Secondary Analyses

Adverse events from date of enrollment up to last contact with patients will be presented for the full study duration and separately for events that occur on- or post-treatment. In particular, safety data will be summarized and listed for all treated patients using the NCI CTCAE version 4.0. All on-study AEs, drug-related AEs, SAEs, and drug-related SAEs will be tabulated using worst grade per NCI CTCAE v4.0 criteria by system organ class and MedDRA preferred term. On-study laboratory parameters including hematology, chemistry, liver function, thyroid function, and renal function will be summarized using worst grade per NCI CTCAE v4.0 criteria.

In addition to reporting number and percentages of patients with adverse events, incidence density rates may be reported for repeated adverse events that vary by duration of study participation. Reporting of 95% confidence intervals for incidence density rates will be based on the Poisson distribution.

[REDACTED]

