6.2.1 Nonserious Adverse Event Collection and Reporting

The collection of nonserious AE information should begin at initiation of study drug. All nonserious adverse events (not only those deemed to be treatment-related) should be collected continuously during the treatment period and for a minimum of 100 days following the last dose of study treatment.

Nonserious AEs should be followed to resolution or stabilization, or reported as SAEs if they become serious (see [Section 6.1.1](#)). Follow-up is also required for nonserious AEs that cause interruption or discontinuation of study drug and for those present at the end of study treatment as appropriate. All identified nonserious AEs must be recorded and described on the nonserious AE page of the CRF (paper or electronic).

Completion of supplemental CRFs may be requested for AEs and/or laboratory abnormalities that are reported/identified during the course of the study.

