8 STATISTICAL CONSIDERATIONS

The study will include patients with histologically confirmed stage III (unresectable) or stage IV melanoma and progression after prior treatment containing an anti-CTLA-4 monoclonal antibody treated with nivolumab (BMS-936558) at a dose of 3 mg/kg every 2 weeks. Patients will be treated with 3 mg/kg of nivolumab IV every 2 weeks for a maximum of 24 months.

Based on the Performance Status of the patients, there are 2 pre-defined cohorts: Cohort 1, enrolling patients with progression after prior treatment containing an anti-CTLA-4 monoclonal antibody and Performance Status 0-1 (n is at least 640, 85% of the minimum of the 735 screened) and Cohort 2, enrolling patients with progression after prior treatment containing an anti-CTLA-4 monoclonal antibody and Performance Status 2 (n is at the most 160, 85% of the maximum of the 185 screened; a minimum of 50 patients will be enrolled).

A patient who meets the screening criteria will be treated for a maximum of 24 months with safety follow-up at 30 [± 7] and 70-84 [± 7] days from first follow-up visit post-treatment. With an expected screening failure rate of 15%, a maximum total of about 800 patients (640 PS1 and 160 PS2) will be treated.

The number and percentage of patients with high-grade, treatment-related, select adverse events and their characteristics will be reported overall and by subgroups and during and off-treatment. Overall survival is defined as the time between the start of treatment and the date of death due to any cause. A patient who has not died will be censored at last known date alive. OS will be followed up while patients are on the study drug and every 3 months via in-person visits or phone contact after patients discontinue study drug.

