In order to derive the time-to resolution, overlapping or contiguous select AEs within a specific category (defined in [Table 5](#)) will be collapsed into what will be termed “clustered” select AEs. For example, if a subject (without pre-treatment AE) experienced an AE from 1st to 5th January, another AE (with different PT but within same category) from 6th to 11th January and same AE from 10th to 12th January, these will be collapsed into one clustered select AE from 1st to 12th January. [Table 4](#) is summarizing key derivation steps for each type of clustered select AEs.

Time-to resolution of select AE (any grade) for a specific category is defined as the longest time from onset to complete resolution or improvement to the grade at baseline among all clustered select AEs in this category experienced by the subject. Events which worsened into grade 5 events (death) or have a resolution date equal to the date of death are considered unresolved. If a clustered select AE is considered as unresolved, the resolution date will be censored to the last known date alive. Improvement to the grade at baseline implies that all different AE events in the clustered

select adverse event should at least have improved to the corresponding (i.e with same preferred term) baseline grade. This measure is defined only for subjects who experienced at least one select AE in the specific category.

The time-to resolution of select AE (grade 3-5) for a specific category is defined similarly with an onset date corresponding to a grade 3-5 select AE.

Time-to resolution of drug-related select AE (any grade or grade 3-5) is defined similarly but restricted to drug-related select AE.

The time-to resolution of select AE (any grade or grade 3-5, drug-related or all) where immune modulating medication was initiated is defined similarly with the additional condition that the subject started an immune modulating medication during the longest select AE resolution period.

Time-to resolution for a specific subcategory is defined similarly but restricted to event of this subcategory.

Table 4: Derivation of Clustered Select AE

Type of clustered select AE	Derivation
Any grade	
 • Collapse any on-treatment select AE from the same category
Drug-related of any grade	
 • Collapse any on-treatment drug-related select AE from the same category

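### Planned Poisson intervals for optional rates of repeated adverse events make no allowance for clustering within patients, and will be too narrow for common recurrent events if such clustering exists

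*Protocol*

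**What the plan says.** Protocol 8.4.2.2 states that "incidence density rates may be reported for repeated adverse events that vary by duration of study participation". The next sentence gives the interval: "Reporting of 95% confidence intervals for incidence density rates will be based on the Poisson distribution". The analysis is therefore optional, but its interval method is fixed if it is run.

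No robust or clustered variance, negative binomial or quasi-Poisson model, or bootstrap is named for these rates in either document. The SAP does not mention incidence density. SAP 7.6.3 lists multiple adverse events among the analyses delegated to a Core Safety SAP, which is not among the documents reviewed.

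SAP Appendix 1 expects one patient to have several related records. It merges "overlapping or contiguous select AEs within a specific category" into one episode, but only to derive time to resolution.

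The primary analysis is a different quantity. Protocol 8.4.2.1 reports the "number, percentage of patients, and 95% confidence intervals for the percentage with these select adverse events during and off-treatment overall and by cohort", so each patient counts once.

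**The concern.** A Poisson interval sets the variance of the event count equal to its mean. That is right when all patients share one rate and events are independent. The documents give reason to doubt both conditions.

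- **Unequal rates.** The trial combines ECOG 0–1 with ECOG 2 (Protocol Table 3.1-1). It also admits at least 40 patients with earlier Grade 3–4 reactions to anti-CTLA-4 therapy (Protocol 3.3.1), and SAP 6.4 singles out patients with autoimmune disease and with previous immune-related events.
- **Linked records.** SAP Table 5 lists raised ALT, raised AST, raised transaminases and hepatitis as separate hepatic terms, so one episode can produce several records. The worked example in Appendix 1 turns three records into one episode. No such merging is stated for rates.

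If either feature is present, the variance exceeds the mean, and a nominal 95% interval around a safety rate, overall or by cohort, is narrower than it should be. Informal comparison of cohorts would then suggest more certainty than the data carry.

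**Working it through.** **Plan figure.** Neither document gives an incidence density rate, count, person-time or interval, so there is nothing to reproduce. The nearest figures, the patient-level intervals in Protocol 8.1, do reproduce with exact binomial limits: 3/640 gives 0.10%–1.36% (stated 0.1%–1.4%) and 2/640 gives 0.04%–1.12% (stated 0%–1.1%).

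**Inputs from the documents (Protocol 8 and 6.2.1).**
- Size: "a maximum total of about 800 patients (640 PS1 and 160 PS2) will be treated"; for Cohort 2, "a minimum of 50 patients will be enrolled".
- Exposure: "A patient who meets the screening criteria will be treated for a maximum of 24 months".
- Collection of nonserious events continues "for a minimum of 100 days following the last dose of study treatment".

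**Assumptions (not in the documents).**
- Mean events per patient, mu.
- Gamma frailty with mean 1 and variance theta.
- Follow-up T exponential with mean 0.6 years, capped at 2 years, plus 100 days (0.274 years).

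**Formula.** Let phi be the ratio of the true variance of the count to its Poisson variance.
- phi = 1 + theta × mu × g, with g = E[T²]/E[T]² for unequal follow-up.
- Mean of the capped part: 0.6 × (1 − e^(−2/0.6)) = 0.579; its variance is 0.274.
- E[T] = 0.579 + 0.274 = 0.852 (unrounded inputs), so g = 1 + 0.274/0.852² = 1.377.
- The Poisson standard error is too small by √phi.
- Coverage is about 2Φ(1.96/√phi) − 1.

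For example, mu = 0.5 and theta = 1 give phi = 1 + 0.5 × 1.377 = 1.689, √phi = 1.30 and coverage 86.9%.

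**Results at n = 640** (simulation: 2,000 trials per scenario, exact Poisson limits against a patient-level sandwich interval on the log rate; Monte Carlo standard error √(0.8 × 0.2/2000) = 0.9 points at 80%):

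| mu | theta | phi | √phi | Coverage, formula | Poisson, simulated | Robust, simulated |
|---|---|---|---|---|---|---|
| 0.5 | 0 | 1.00 | 1.00 | 95.0% | 95.4% | 95.1% |
| 0.1 | 2 | 1.28 | 1.13 | 91.7% | 91.7% | 94.3% |
| 0.5 | 1 | 1.69 | 1.30 | 86.9% | 87.2% | 94.4% |
| 0.5 | 2 | 2.38 | 1.54 | 79.6% | 80.5% | 94.9% |
| 1.0 | 1 | 2.38 | 1.54 | 79.6% | 80.8% | 95.3% |

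A separate simulation gave 86%, 81% and 82% for the last three rows, 95% at 3 events per patient with no frailty, and 93%–95% at 0.05 events per patient.

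**Linked records without frailty.** If each episode yields m records and records are counted, phi = E[m²]/E[m], whatever the event rate.
- Half of episodes with two records: 2.5/1.5 = 1.67, coverage 87%.
- All with two: 4/2 = 2, coverage 83%.
- One, two or three equally likely: 4.67/2 = 2.33, coverage 80%.

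The distribution of m is assumed.

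**Plausible event counts.** In Protocol Table 1.4.2-1 (study CA209003, 306 patients), the any-grade treatment-related column, without its first row, sums to 364, or 364/306 = 1.2 patient-term occurrences per patient. High-grade select events are far rarer: Protocol 1.4.3 reports under 5% of nivolumab patients in CA209037.

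**Small cohorts.** At n = 50 and 0.05 events per patient (50 × 0.05 = 2.5 events expected), the log-rate sandwich interval is undefined in 8%–10% of trials because no event occurs, and it covers in only about 87%–88%. At 0.02 events it is undefined in about 37%. Exact Poisson covers about 98% at 0.05. At 0.1 events (5 expected) the sandwich interval covers 95%–96%.

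**The case against.** - **Several events per patient do not break the Poisson assumption.** This stands. A reader might infer that repeated counting alone makes the interval too narrow, but with a common rate and independent events coverage is 95% even at 3 events per patient. Unequal rates or linked events do the damage.
- **No interval in the documents is wrong.** Also true. Only a method is given, and the frailty variance, mean counts and follow-up pattern are all assumed, so the actual shortfall cannot be computed from the documents.
- **The effect is small for the events this trial targets.** It stands for high-grade select events under frailty. It does not cover common or all-event rates, nor rates that count linked records.
- **The analysis is optional and absent from the SAP.** True, and the Core Safety SAP might say more. But the protocol names the Poisson distribution outright and gives no adjustment.
- **No named endpoint or planned test depends on it.** True. The primary and secondary endpoints are patient incidence, times to onset and resolution, OS and ORR. A reader might infer that the main safety conclusion or formal subgroup comparisons are at risk; the documents do not support that.
- **A blanket robust variance fails with sparse data.** This stands and shapes the remedy. Cohort 2 may have only 50 patients, and the minimum for uveal melanoma is 30.

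**Conclusion.** The point holds conditionally. The protocol fixes an interval that is valid only without clustering, in a population and with a coding scheme that make clustering plausible. Under the stated frailty and follow-up assumptions at n = 640, coverage falls to about 81%–86% at 0.5 events per patient (theta 2 to 1) and about 82% at 1 event (theta 1), with simulation runs differing by a point or so. There is no loss at theta = 0, and under frailty little at 0.05 events per patient (93%–95%). The consequence is confined to an optional secondary description of recurrent events. The primary endpoint is untouched.

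**What to change.** Replace the last sentence of Protocol 8.4.2.2, and carry the same text into the SAP:

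> If incidence density rates of repeated events are reported, 95% CIs will use a patient-level robust (sandwich) variance from a log-linear rate model with log person-time as offset. Where fewer than a pre-set number of patients have events, including none, the exact Poisson CI will be given and labelled as assuming no clustering. Exact Poisson CIs will also be used for first-event rates with person-time ending at that event.

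The minimum number of patients with events should be fixed before database lock; the n = 50 results above are a guide. The robust variance works on patient totals, so it covers both unequal rates and linked records.

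The cost is a changed procedure option, one small-count rule and somewhat wider intervals where clustering exists (standard error larger by about 1.3 to 1.5 in the scenarios at 0.5 events per patient). With no clustering, the simulated ratio to the Poisson standard error was 1.00 at n = 640. No new data are needed.
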